6.6.3 Safety data

From CTP Section 7.5: *With respect to safety evaluations, it is not planned to impute missing values.*

The only exceptions where imputation might be necessary for safety evaluation are AE dates and start and stop dates for concomitant medications. Missing or incomplete AE dates are imputed according to BI standards (see BI-KMED-BDS-HTG-0035 (3)).

Partial start and stop dates for concomitant medications will be imputed to enable subsequent calculation (but not for display) by the following "worst case" approach:

- If the day of the end date is missing, then the end date is set to last day of the month (or to the patient's trial completion date, if it is earlier than the last day of the month).
- If the day and month of the end date are missing then the end date is set to 31st of December of the year (or to the patient's trial completion date, if it is earlier than the 31st of December of the year).
- If the day of the start date is missing the start date is set to first day of the month.
- If the day and month of the start date are missing then the start date is set to 1st January of the year.
- All other cases need to be assessed by the trial team on an individual basis, using the above points as guidance.

6.6.4 Time since first diagnosis

For incomplete information on the date of first diagnosis, time since first diagnosis will be calculated as follows:

- If the year of first diagnosis is unknown, time since first diagnosis will be set to missing. Note: Every effort should be made to have at least data on year of the first diagnosis populated.
- If day and month of the first diagnosis are unknown, time since first diagnosis will be calculated as if diagnosed on the 30th June of that year.
- If only the day of the first diagnosis is unknown, time since first diagnosis will be calculated as if diagnosed on the 15th of that month.

Information on the time since first diagnosis will be imported from the database of the parent trial (1368-0032).

6.7 BASELINE, TIME WINDOWS AND CALCULATED VISITS

Measurements reported with date and time and taken prior to start of administration of trial treatment will be considered pre-treatment values. Measurements reported with a date only (and no time) and taken on the day of first administration of trial treatment will also be considered pre-treatment values. These pre-treatment values will be assigned to visits according to the nominal visit number as recorded on the eCRF or as provided by the laboratory. For definitions used in Safety analyses, refer to [Section 7.8](#).

There will be two different baseline definitions used in the analyses:

1. Baseline for this extension trial – defined as the last measurement recorded before the first trial medication administration in this study.

2. Baseline for the parent trial (1638-0032) – defined as the measurement recorded at randomisation visit (Visit 2) of the parent trial. If the data at Visit 2 is missing, then the data from Visit 1 of the parent trial will be considered baseline.

Two separate analyses will be conducted, using the baselines as defined above.

Measurements taken after start of administration of trial treatment will be considered either on- or off-treatment values based on the definition in [Section 6.1](#), and will be assigned to visits for statistical analysis, if applicable, as defined below.

Analysis of AE data, concomitant medication or non-drug therapies will not be based on visits. Therefore, no assignment to time windows will be necessary for such data.

For derivation of the last value on treatment, minimum value on treatment, and maximum value in the trial phase, all values from the relevant phase (whether or not collected in any time window; see [Table 6.1: 1](#) for definition of the trial phases) will be considered; these will be derived for analysis of laboratory and vital signs data. For identification of potentially clinically significant abnormal laboratory values, all values (whether or not selected in any time window) before the date of EoS Participation visit will be considered.

A graphical analysis of the ALT and total bilirubin will be performed (so called eDISH plot) based on the available data obtained during the on-treatment period.

All other safety, efficacy and biomarker measurements will be assigned to visits based on extended time windows around the planned visit dates, defined relative to the day of first trial treatment (which is scheduled for Visit V2). These extended time windows are defined in [Table 6.7: 1](#).

Table 6.7: 1 Time windows for assignment of efficacy, safety lab, vital signs, and biomarker measurements to visits for statistical analysis

Visit number / name	Visit label	Planned day	Time window (Days)				
			Window (per CTP)	Start (per CTP)	End (per CTP)	Start (extended)	End (extended)
V1	Day 1	Day 1	n/a	1 ^A	1	1 ^A	1
V2	Week 4	Day 29	+/- 14	15	43	2	43
V3	Week 8	Day 57	+/- 14	44	71	44	71
V4	Week 12	Day 85	+/- 14	72	99	72	99
V5	Week 16	Day 113	+/- 14	100	127	100	127
V6	Week 20	Day 141	+/- 14	128	155	128	155
V7	Week 24	Day 169	+/- 14	156	183	156	183
V8	Week 28	Day 197	+/- 14	184	211	184	211
V9	Week 32	Day 225	+/- 14	212	239	212	239
V10	Week 36	Day 253	+/- 14	240	267	240	267
V11	Week 40	Day 281	+/- 14	268	295	268	295
V12	Week 44	Day 309	+/- 14	296	323	296	323
V13	Week 48	Day 337	+/- 14	324	351	324	351
V14	Week 52	Day 365	+/- 14	352	379	352	379
V15	Week 56	Day 393	+/- 14	380	407	380	407
V16	Week 60	Day 421	+/- 14	408	435	408	435
V17	Week 64	Day 449	+/- 14	436	463	436	463
V18	Week 68	Day 477	+/- 14	464	491	464	491
V19	Week 72	Day 505	+/- 14	492	519	492	519
V20	Week 76	Day 533	+/- 14	520	547	520	547
V21	Week 80	Day 561	+/- 14	548	575	548	575
V22	Week 84	Day 589	+/- 14	576	603	576	603
V23	Week 88	Day 617	+/- 14	604	631	604	631
V24	Week 92	Day 645	+/- 14	632	659	632	659
V25	Week 96	Day 673	+/- 14	660	687	660	687
V26	Week 100	Day 701	+/- 14	688	715	688	715
V27	Week 104	Day 729	+/- 14	716	743	716	743
...
V52	EoT	Day 1429	+/- 14	1415	1443	1415	1443
V53	EoS	Day 1541	+/- 14	1528	1555	1444	1555/EoT+ 16weeks

Days are counted relative to the day of first treatment, which is defined as Day 1.

^A Note that measurements made at Day 1 and assigned to the on-treatment period (because mistakenly made after start of injection of trial treatment) via assessment on date and time (i.e. safety laboratory) will not be assigned to Day 1. Such data will be listed only.

Repeated and unscheduled efficacy, safety and biomarker measurements will be handled similarly to scheduled measurements and will also be assigned to a time window depending upon the date of measurement.

Only one observation per time window will be selected for statistical analysis at a particular visit – the value which is closest to the protocol planned visit day will be selected. If there are two observations which have the same difference in days to the planned day, the later value will be selected. If there are two observations on the same day, the worst value will be selected.

Assignment of efficacy observations to visits based on time windows will be based on the non-imputed (observed) data.

For visits without an assigned value based on time windows, a value will thereafter be imputed as defined in [Section 6.6](#). Imputation of efficacy endpoints, when applicable, will be performed based on all available observations obtained during the on-treatment period, irrespective of whether the observation was selected in any time window.

In addition, separate analyses will be performed using the parent trial baseline. Baseline value will then be defined the same way as in the parent trial (1368-0032) and will be taken from that parent trial.

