1.2.1.1 Residual Effect Period

The Residual Effect Period (REP) of BI 655130 is 16 weeks. This is the period after the last dose with measurable drug levels and/or pharmacodynamic effects still likely to be present.

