6.2.3 End of Treatment and Trial Completion

For all treated patients termination of trial medication and trial completion must be recorded on the corresponding eCRF.

For the comprehensive list of the trial procedures required at the EOT and the EOS visits please refer to [Flow Chart](#).

The EOS visit must be performed 16 weeks after the date of last drug administration.

Early Treatment and Trial Discontinuation:

If trial treatment is discontinued prematurely prior to the planned [Flow Chart](#) EOT visit, every effort should be made to have the patient return and undergo the procedures for the EOT visit as well as the EOS visit 16 weeks after the last study drug administration as outlined in the [Flow Chart](#).

Patients who are unable to physically return to the study site for the EOT and EOS visits should be contacted by the site by phone to collect information pertaining to adverse events and changes to concomitant therapy.

Trial Completion:

Trial completion is defined as a patient having reached the EOS visit within the specified window per protocol.

Treatment Completion:

Treatment completion is defined as a patient completing Visit 52 which is the EOT visit after receiving approximately 4 years of treatment

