7.2.5 Safety analyses

Adverse events will be coded using the Medical Dictionary for Drug Regulatory Activities (MedDRA). Standard BI summary tables and listings will be produced. All adverse events with an onset between start of treatment and end of the REP, a period of 16 weeks after the last dose of trial medication, will be assigned to the on-treatment period for evaluation.

All treated patients will be included in the safety analysis. In general, safety analyses will be descriptive in nature and will be based on BI standards. No hypothesis testing is planned.

Statistical analysis and reporting of adverse events will concentrate on treatment-emergent adverse events, i.e. all adverse events occurring between start of treatment and end of the REP. Adverse events that start before first drug intake and deteriorate under treatment will also be considered as 'treatment-emergent'.

Frequency, severity, and causal relationship of adverse events will be tabulated by system organ class and preferred term after coding according to the Medical Dictionary for Drug Regulatory Activities (MedDRA).

Laboratory data will be analysed both quantitatively as well as qualitatively. The latter will be done via comparison of laboratory data to their reference ranges. Values outside the reference range as well as values defined as clinically relevant will be summarised. Groups (defined in [Section 7.2.1](#)) will be compared descriptively with regard to distribution parameters as well as with regard to frequency and percentage of patients with abnormal values or clinically relevant abnormal values.

Vital signs, physical examinations, or other safety-relevant data observed at baseline, during the course of the trial and at the end-of-trial evaluation will be assessed with regard to possible changes compared to findings before start of treatment.

[REDACTED]

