6. GENERAL ANALYSIS DEFINITIONS

6.1 TREATMENT(S)

For basic study information on the treatment to be administered, assignment to treatment, and selection of dose, cf. Section 4 of the CTP.

All patients will receive subcutaneous doses of 600 mg of BI 655130 solution for SC injection (every four weeks).

The following trial phases are defined:

Table 6.1: 1 Flow chart of trial phases

Trial phase	Description	Start (included)	End (excluded)
Open label Treatment phase	On-treatment period	Date of start of injection of first study drug (Day 1)	EoT visit date + 1 day
Follow-up phase	Off-treatment follow-up period	EoT visit date + 1 day	Date of EoS Participation visit + 1 day

Dates are defined individually per patient. If more than one date is associated with a specific visit, measurements associated with a specific date are assigned to a study analysis phase according to the rules specified in the table. An analysis phase will not extend beyond the start date of the following phase.

EoT = End of treatment; EoS = End of study;

Patients who discontinue the treatment but will continue on trial visits will be included in analyses with the available data. For patients who discontinue the trial prematurely only available data will be used in the analyses.

The time windows for data presentation in the analysis are described in [Table 6.7: 1](#).

Treatment group will be labelled as follows: "**Speso 600 mg SC q4w**" (i.e., patients receiving BI 655130 600 mg). In addition, the descriptive statistics will be presented for the following groups:

- By treatment received in the parent trial (1368-0032):
 - "Placebo" followed by "Speso 600 mg SC q4w"** – patients who were randomised to receive placebo in the double-blind period of the parent trial and received Speso treatment in the open-label period of the parent trial
 - "Placebo" followed by "no Speso 600 mg SC q4w"** – patients who were randomised to receive placebo in the double-blind period of the parent trial and

didn't receive Speso treatment in the open-label period of the parent trial (but didn't discontinue the parent study prematurely)

- **"Speso 600 mg SC q4w" followed by "Speso 600 mg SC q4w"** – patients who were randomised to receive active treatment (Speso) in the double-blind period of the parent trial and received Speso treatment in the open-label period of the parent trial

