7.8.2 Laboratory data

The analyses of laboratory data will be descriptive in nature and will be based on BI standards (5). Note that data from the central Laboratory will be used for all displays described below, unless otherwise specified.

For continuous safety laboratory parameters, normalized values will be derived. Normalisation means transformation to a standard unit and to a standard reference range. The process of normalisation, handling of repeat values at the same visit for by-visit displays, as well as standard analyses for safety laboratory data are described in the BI guidance for the “Handling, Display and Analysis of Laboratory Data” (5). All analyses considering multiple times of the ULN (as described below) will be based on standardized and not normalized values. For continuous safety laboratory parameters, differences to baseline will be calculated.

Only patients with at least one available post-baseline value will be included in the analysis of an individual laboratory parameter. All individual laboratory data will be listed. Values outside the reference range will be flagged.

Descriptive statistics of laboratory values over time and for the difference from baseline (see Section 6.7) will be based upon normalised values and provided by visit, including summaries of the last value on treatment, the minimum value on treatment and maximum value on treatment.

Laboratory values will be compared to their reference ranges; shift tables will be provided for the number of patients with a specific RCTC grade at baseline versus the grade at the last measurement on treatment, as well as the worst grade on treatment. These analyses will be based on standardized laboratory values.

Potentially clinically significant abnormalities will be identified based on BI standard rules which are based on normalized converted lab values, i.e. using SI units. These rules will be listed in the SDL appendix of the CTR. Frequency tables will summarize the number of patients with potentially clinically significant abnormalities. Patients having an abnormal lab value at baseline will be presented separately. A separate listing will present potentially clinically significant abnormal lab values.

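### SAP 6.7 stops the search for potentially clinically significant laboratory values the day before the EoS visit, so any value dated on the EoS day is left out of that table and listing

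*SAP*

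**What the plan says.** SAP 6.7 sets the data cut for PCSA identification: "all values (whether or not selected in any time window) before the date of EoS Participation visit will be considered". SAP 7.8.2 describes what is built on it: "Frequency tables will summarize the number of patients with potentially clinically significant abnormalities", plus a separate listing. It gives no cut-off of its own.

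SAP Table 6.1:1 ends the follow-up phase, in a column headed as an excluded end, at "Date of EoS Participation visit + 1 day". The EoS day is therefore inside follow-up. SAP Table 6.7:1, titled "Time windows for assignment of efficacy, safety lab, vital signs, and biomarker measurements to visits for statistical analysis", has a row for V53 (EoS).

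On timing, Protocol 6.2.3 states: "The EOS visit must be performed 16 weeks after the date of last drug administration". Protocol 1.2.1.1 states: "The Residual Effect Period (REP) of BI 655130 is 16 weeks". The Years 2-4 flow chart shows V53 (EOS, Week 220) as the only visit after V52 (EOT, Week 204).

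**The concern.** The two date conventions in the SAP differ by one day, and that day is the EoS visit. Other laboratory summaries (last, minimum and maximum value on treatment, RCTC shift tables, the eDISH plot) are tied to the on-treatment period, which Table 6.1:1 closes at the EoT visit. The PCSA rule is not tied to it and runs on towards EoS. It is therefore one of the few rule-based patient counts that could cover the residual effect period. By stopping the day before EoS, it takes in unscheduled samples from that period but not the one scheduled visit.

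This is a long-term safety trial with widely spaced scheduled laboratory tests. If blood is drawn at EoS, an abnormality that first meets the criteria there is absent from the table meant to count it. A programmer following the text would apply the strict inequality.

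**Working it through.** The plan gives no figure to reproduce. The check compares two date rules and counts scheduled samples.

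**1. Planned days** (Years 2-4 flow chart; SAP Table 6.7:1)
- EOT, Week 204: 1 + 204 × 7 = Day 1429.
- EOS, Week 220: 1 + 220 × 7 = Day 1541.
- Difference: 1541 − 1429 = 112 days = 16 weeks. For a completer, whose last dose is at EOT, EoS falls at the end of the residual effect period.

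**2. A sample dated Day 1541 under each rule**

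| Rule | Condition | Day 1541 |
|---|---|---|
| SAP 6.7, PCSA identification | day < EoS date: 1541 < 1541 | excluded |
| SAP Table 6.1:1, follow-up phase | EoT + 1 ≤ day < EoS + 1: 1430 ≤ 1541 < 1542 | included |

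**3. Coverage of follow-up**
- Table 6.1:1: Days 1430 to 1541, which is 1542 − 1430 = 112 days.
- SAP 6.7: Days 1430 to 1540, which is 1541 − 1430 = 111 days.
- The one day lost is that of the only scheduled post-EoT visit.

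**4. Scheduled safety laboratory samples after baseline**

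The Year 1 flow chart places safety laboratory tests at V1, V7 (type D) and V13 (type E). The Years 2-4 chart repeats the schedule by visit type, so the D and E visits are V7, V13, V20, V26, V33, V39 and V46: Weeks 24, 48, 76, 100, 128, 152 and 180. Assume draws at EOT (Week 204) and EOS (Week 220) as well.
- Completer: 7 + 2 = 9 samples. The EoS sample is 1 of 9 (11%).
- Patient stopping before Week 24: EOT and EOS only. The EoS sample is 1 of 2 (50%).
- Gaps in weeks, from Day 1: 24, 24, 28, 24, 28, 24, 28, 24, then 16 from EOT to EOS.
- If no safety laboratory test is scheduled at EoS, the scheduled loss is zero in both cases. Any laboratory value that is nevertheless dated on the EoS day remains excluded.

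**The case against.** **A draw at EoS is not shown.** Protocol 6.2.3 says only: "For the comprehensive list of the trial procedures required at the EOT and the EOS visits please refer to" the flow chart, and that grid is not visible in the available text, which is no fault of the plan. The V53 row in SAP Table 6.7:1 does not settle it. The table is a shared grid that also has rows for visits such as V2 and V3, where the Year 1 flow chart schedules no safety laboratory test. This objection stands: a draw at EoS is likely but must be stated as an assumption.

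**EoS values are handled elsewhere.** A reader might infer that they are never examined. The documents do not support that. SAP 7.8.2 lists all individual laboratory data and flags out-of-range values. It plans by-visit summaries, for which Table 6.7:1 has an EoS window, and it states no EoS cut-off for the AST/ALT threshold tables. Under Protocol 5.2.3 the investigator evaluates the laboratory reports and records clinically relevant findings as adverse events. This also stands, and confines the gap to the rule-based PCSA table and listing. Listings and case-by-case judgement still do not replace a count made under a fixed rule.

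**There is no breach of the protocol.** Protocol 7.2.5 says that certain data "at the end-of-trial evaluation will be assessed with regard to possible changes compared to findings before start of treatment", and a reader might take this as a requirement that the SAP contradicts. The sentence opens with vital signs and physical examinations and then refers to other safety-relevant data. Laboratory data have their own paragraph just before it, with no end-of-trial requirement. The sentence does not prescribe what enters a PCSA table.

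**Table 6.1:1 defines phases and does not set the PCSA cut-off.** True: the mismatch may be no more than a dropped + 1 day. That explains how the wording arose, but the rule as written still excludes the EoS day.

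**The analyses are exploratory and the primary endpoint is untouched.** Also true. It limits the consequence to the accuracy of one safety display.

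**Conclusion.** The concern holds in a limited form. As written, SAP 6.7 leaves any laboratory value dated on the EoS day out of the PCSA frequency table and listing, nothing in SAP 7.8.2 restores it, and the convention differs from Table 6.1:1.

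If safety laboratory tests are drawn at both EOT and EOS, 1 of 9 scheduled post-baseline samples is lost for a completer and 1 of 2 for a patient who stops before Week 24. The PCSA frequency can then be too low. It is not necessarily too low: only patients who first meet the criteria at EoS are missed, and the documents give no rate from which to estimate how many that would be.

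The documents do not support saying that EoS results go unscreened, that an EoS draw is established, or that the SAP violates Protocol 7.2.5. The primary endpoint, treatment-emergent adverse events at Week 48, does not depend on this rule.

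**What to change.** In SAP 6.7, change the PCSA cut-off so that it takes all values *up to and including the date of the EoS Participation visit (i.e. before EoS date + 1 day)*, in line with Table 6.1:1.

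The cost is one phrase in the SAP and one inequality in the program, with no new data. If the EOT/EOS flow chart turns out to schedule no safety laboratory test at EoS, the change does no harm and still captures any laboratory value obtained that day.

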6.2.2 Treatment period

After Visit 1, the patient will return for 51 additional visits during the treatment period. The duration between visits is 4 weeks. At every visit study drug will be administered.

If the patient completes this 4 year study, the last study drug administration will be at Visit 52 (EOT).

Drug administration and rules for early/late visits

It's important for the patient to adhere to the visit schedule per the [Flow Chart](#). The visit schedule should always align with Visit 1.

The IRT system has been set up to make sure that a patient does not receive 2 doses of medication in less than a 14 day period.

In these scenarios, the patient should conduct the visit but skip the dose. The patient should be administered the dose at the next scheduled visit.

Pregnancy Testing

Urine pregnancy testing for all woman of childbearing potential will be conducted on-site prior to every dosing and must be negative to receive study drug. A positive urine test must be confirmed with a serum pregnancy test at the central laboratory.

See the [Flow Chart](#) for details of all procedures required at each visit.

Unscheduled visits

If a patient suspects that their AD is worsening in between the protocol specified scheduled visits, they should make an unscheduled visit and return to the clinic/site for assessment. The patient may be called in for additional unscheduled visits due to safety reason at the discretion of the investigator or the sponsor, unless the patient has withdrawn his/her consent. The patient may also contact the site due to safety reason for an unscheduled visit. The unscheduled visit may include additional collection of blood samples for safety reasons. The unscheduled visit may also include additional assessments deemed necessary by the investigator such as laboratory samples, ECGs, or other procedures which were missed at a previous visit. All unscheduled visits should be described (including the reason for the visit) and documented in the medical/source record, and in the eCRF.

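### Unscheduled scores, which worsening AD can prompt, compete equally with the scheduled Week 48 assessment and could tilt Week 48 efficacy towards worse disease

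*SAP*

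**What the plan says.** SAP 6.7 puts efficacy measurements into visit windows by date. The Week 48 row of Table 6.7:1 reads "V13 Week 48 Day 337 +/- 14 324 351 324 351": planned Day 337, window Days 324 to 351. For extra measurements the section says: "Repeated and unscheduled efficacy, safety and biomarker measurements will be handled similarly to scheduled measurements and will also be assigned to a time window". One observation per window is analysed, and "the value which is closest to the protocol planned visit day will be selected". Two tie rules follow: "If there are two observations which have the same difference in days to the planned day, the later value will be selected", and "If there are two observations on the same day, the worst value will be selected". No rule favours the scheduled visit.

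Protocol 6.2.2 gives the reasons for an unscheduled visit. The first is disease worsening: "If a patient suspects that their AD is worsening in between the protocol specified scheduled visits, they should make an unscheduled visit". The section also covers safety: "The patient may be called in for additional unscheduled visits due to safety reason at the discretion of the investigator or the sponsor". Patients may contact the site themselves for a safety reason too. The content of the visit is left to the investigator, with examples "such as laboratory samples, ECGs, or other procedures which were missed at a previous visit". EASI, SCORAD and IGA are neither required nor excluded.

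All five secondary endpoints (Protocol 2.1.3; SAP 5.2.2) are Week 48 EASI, SCORAD or IGA measures.

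**The concern.** A window rule based only on dates is harmless when the dates have nothing to do with the outcome. Here they can. The protocol brings in a patient who feels worse and has no matching rule for a patient who feels better. A score taken at such a visit enters the Week 48 window on equal terms, and if it lies nearer Day 337 it replaces the assessment that the protocol scheduled. For example, a patient seen for V13 on Day 330 who meets EASI75, and who returns with a flare on Day 340, has the flare score analysed as Week 48 (3 days from plan against 7).

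The selection can therefore depend on the outcome. This is a single-arm trial, so there is no comparator in which the effect would cancel. Continuous endpoints use observed data only (SAP 6.6.2), so a substituted value goes straight into the mean. The additional observed-data tables for binary endpoints do not help, because the window selection has already been made. The SAP text available contains no analysis restricted to scheduled visits.

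**Working it through.** The plan states no figure for this effect, so there is none to reproduce. Its window arithmetic is consistent: Week 48 is 48 × 7 + 1 = Day 337, and Days 324 to 351 run from 13 days before to 14 days after, 28 days in all.

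**Inputs from the documents**
- Rule: closest to Day 337; equal distance goes to the later value (SAP 6.7).
- Patients: about 40, at most 45 (Protocol 7.5).

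**Assumptions**
- One scheduled V13 score and one unscheduled score, on different days in the window, each day equally likely within the range shown.
- 5% to 15% of patients have such an unscheduled score.

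**Step 1: days that displace a given V13.** Of the other 27 days in the window:
- V13 on Day 337: 0 days.
- V13 k days late: 2k − 1 days are closer, and the equally distant earlier day loses the tie.
- V13 k days early: the same 2k − 1 days, plus the equally distant later day, which wins the tie, so 2k.

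V13 on Day 330 (k = 7, early) gives 14/27 = 51.9%. V13 on Day 351 (14 days late) gives 27/27.

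**Step 2: average over V13 dates.** Each pair of dates k days either side contributes (2k − 1) + 2k = 4k − 1.
- Within 3 days: 3 + 7 + 11 = 21; 21/(7 × 27) = 21/189 = 11.1%.
- Within 7 days: 4 × 28 − 7 = 105; 105/(15 × 27) = 105/405 = 25.9%.
- Whole window: 4 × 91 − 13 = 351 for k = 1 to 13, plus 27 for Day 351, makes 378; 378/(28 × 27) = 378/756 = 50%.

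**Step 3: expected number of replaced Week 48 values.** With 40 patients, 5% is 2 and 15% is 6.

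| V13 timing | Chance | 2 patients | 6 patients |
|---|---|---|---|
| Day 337 | 0% | 0 | 0 |
| Within 3 days | 11.1% | 0.2 | 0.7 |
| Within 7 days | 25.9% | 0.5 | 1.6 |
| Whole window | 50% | 1.0 | 3.0 |

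**Step 4: effect on the results.** One responder turned non-responder moves the overall rate by 1/40 = 2.5 points (1/45 = 2.2). Three would move it by 7.5 points, but only with V13 spread evenly over the whole window, 15% of patients affected, and every replaced patient a responder at V13 who then flips. For percent change in EASI, one replaced value that differs by 25 to 50 points (assumption) moves a mean over 40 patients by 25/40 = 0.6 to 50/40 = 1.25 points.

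Same-day pairs are left out of the enumeration. There the worst value is taken, so a worse second score on the same day displaces V13 even on Day 337.

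**Step 5: after the fix.** With the scheduled score first, the chance of replacement is 0 in every row.

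**The case against.** The rule is prespecified and based on dates, the analyses are exploratory with no testing, and any bias runs against the drug. Visits are meant to stay aligned with Visit 1 (Protocol 6.1 and 6.2.2), so the 50% case is probably pessimistic. Flares are not lost: individual values are listed (SAP 7), worsening of the underlying disease is recorded as an AE (Protocol 5.2.6.1.1), and the reason for each unscheduled visit is documented. Some flaring patients would count as non-responders anyway, because rescue medication ends trial treatment (Protocol 4.2.2.1) and binary data after the last dose plus 4 weeks are set to missing (SAP 6.6.2).

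Most of this stands as a limit on size. It does not remove the mechanism. Flares without rescue, and all continuous endpoints, fall outside the last argument. A listing does not correct a summary table, and a bias against the drug is still an error in a descriptive estimate.

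A reader might infer three stronger things that the documents do not support:
- *That unscheduled scores are always driven by flares, so the results are biased.* Safety visits and make-up of missed procedures are also allowed, and a make-up Week 48 score is legitimate. How often a competing score will exist is unknown.
- *That efficacy scores in windows without a scheduled assessment come only from unscheduled visits.* V4 on Day 71 is within ±14 days of Day 85 but falls in the Week 8 window, and V13 on Day 323 falls in the Week 44 window. The SAP also does not say that efficacy tables will be shown for those weeks.
- *That repeat laboratory tests distort the safety results in the same way.* Minimum, maximum and last values on treatment, and significant abnormalities, use all values whether or not selected in a window (SAP 6.7). Repeats at the same visit follow separate sponsor guidance (SAP 7.8.2).

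**Conclusion.** The point holds as a possible bias in the Week 48 secondary efficacy endpoints, towards worse disease. The mechanism and its direction follow from Protocol 6.2.2 and SAP 6.7 read together. The size does not: it depends on how close V13 falls to Day 337, how many patients have a competing score, and how many of those scores are flares. Under the stated assumptions about 0 to 3 of 40 Week 48 values are replaced, each moving the overall responder rate by at most 2.5 points. One patient weighs more in the smaller groups defined by parent-trial treatment or response. The primary endpoint is untouched, because AE analysis is not based on visits (SAP 6.7). This is a cheap improvement to a descriptive analysis and does not threaten the trial's main result.

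**What to change.** In SAP 6.7, add that within a window the scheduled visit's efficacy assessment takes precedence, and that an unscheduled value is used only when no scheduled value exists in that window. This keeps make-up assessments. State that the precedence also overrides the same-day worst-value rule when one score is scheduled and the other is not. The closest, later and worst rules then apply only among values of the same kind. Report the present closest-value rule as a sensitivity analysis for Week 48.

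The cost is one or two sentences, a sort key in the windowing program and one further set of Week 48 tables. The downside is that a flare near V13 will show in the listings, the AE data and the sensitivity analysis, and not in the main Week 48 score.
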